Systematic reviews have shown that researchers have examined interventions for dementia caregivers who provide care in the home, including some that focused on reducing their stress or promoting/preserving health. NIH-funded researchers have engaged in multi-site projects, Resources for Enhancing Alzheimer's Caregiver Health (REACH), since 1995. They have tested educational support groups, behavioral care, skills training programs, family-based

interventions, environmental modifications, computer-based information, and communication services. All of the interventions were found to be superior to control conditions for female versus male caregivers and for caregivers with lower versus higher education. Positive outcomes include fewer depressive and anxious symptoms, greater satisfaction, and better sense of well-being. These studies, however, were limited to caregivers of persons with dementia in the home and did not include caregivers whose family member was living within a facility as proposed in this study. Thus, the interventions were not tested in those caregivers, who are believed to experience similar stress levels and deleterious effects on health. In addition, the interventions tested within the REACH projects did not include the implementation of biofeedback as a means for stress reduction or the teaching skills that constitute resourcefulness as proposed in this study.

Only one study examined biofeedback in caregivers of persons with dementia and it found that biofeedback was feasible and effective for stress management in family caregivers. The study was missing a control group and the sample was very small (N=32) and limited to in-home dementia caregivers whose care recipient attended a senior day care facility. However, systematic review of other intervention studies of dementia caregivers have described beneficial effects on caregiver health and of such skills as cognitive reframing, problem-solving, self-management, and help-seeking, all of which are included in resourcefulness training. Consistent with the personal (self-help) and social (help-seeking) skills taught during resourcefulness training, researchers have identified the need for interventions to assist dementia caregivers to seek out and mobilize social resources while enhancing personal coping effectiveness.

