In addition, agency personnel/health care professionals may nominate a caregiver for the study. We will use snowball recruitment by asking study participants to refer others like them to the study. We will also recruit via the internet using social media sites (e.g. Twitter, Facebook, Instagram, and other online sources).

3. Describe the source (e.g., from what department, EMR, etc.) of the research participants.

Potential study participants (who meet the study criteria) will be recruited through both public and private advocacy agencies, care facilities, support groups, community health centers, health fairs and other community events, print and e-newsletters (e.g. CASE Daily), listservs, local magazines and newspapers, ResearchMatch.com, Alzheimer's Association TrialMatch, and private physician offices in Cuyahoga and 6 adjacent counties in Northeastern Ohio.

4. Describe the methods that will be used to **identify** potential research participants.

When a person contacts the study to be screened, they will receive a screening ID in the Screening and Enrollment log. Contact information will then be collected including date of initial contact, name, telephone number(s), email address(es), and mailing address on all individuals screened will be collected for our screening log; this information will be stored in a password-protected computer file (Box.com).

The project manager or other trained research staff will screen by phone to ensure that caregivers meet all eligibility criteria. We will also be collecting demographic information (gender, race, ethnicity, etc.). All individuals that are screened and asked questions to see if they meet eligibility criteria. At the end of the screening, they will be asked if they would like to consent to be contacted for future research opportunities (those that enroll in the study will also be asked if they consent for future research with the informed consent form). All screening question documentation will be kept in a screening form on REDCap along with screening ID.

After eligibility is verified during phone screening by team member, the consent form will be reviewed verbally, and questions about the study will be answered. The research team

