
Following informed consent, research staff will collect detailed contact information and schedule the first data collection session. The data collection for caregivers sampled involves two structured face-to-face sessions with data collectors. Data will be collected at baseline (T1) and within one month after the 4-week intervention (T2). Measures include dementia symptoms, caregiver reactions, caregiving involvement, dementia knowledge, resourcefulness, heart rate

variability, health risks, and health outcomes, comprising the 156-item questionnaire. Demographic information will also be collected (e.g. occupation, annual income, education, and questions about the care recipient such as age, number of years diagnosed with dementia, specific diagnoses, and questions related to the participant's caring of their family member with dementia). Research assistants will encourage caregivers to respond to items displayed on an iPad/ tablet as they wish, ensuring there are no right or wrong responses. At the first data collection session, the study participant will receive a resource list for Dementia Care support and services in Cuyahoga and surrounding counties.

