The primary study aim (Aim #1) is to examine differences across our three groups of family caregivers of persons with dementia on caregiver health outcomes from pre- to post-intervention. The underlying analyses for A1 are built around the repeated measures analysis of variance (RMANOVA). The primary analysis will be a three group × two time waves RMANOVA. These analyses will compare the three groups: 1) usual care (education), 2) resourcefulness, and 3) biofeedback across two time waves of health risks and physical and mental health outcomes. When using RMANOVA, one not only assesses mean differences across time, but also group differences and the interaction of time × group, which will allow us to test the trend of the means over time across the three groups. The RMANOVA, not only is used to determine if there are mean differences across the two time periods, it also uses orthogonal polynomial contrasts to determine linear trends of the means across time. Orthogonal polynomials are weights assigned to each time period that models a linear trend. RMANOVA will determine if these trends in the means are significant. A linear trend is indicated if there is a steady increase or decline in scores from the first time wave to the second time wave.

The second aim (Aim #2) identifies the responses to usual care (education), resourcefulness training, and biofeedback separately on the three health outcomes between the caregivers of persons with dementia sampled within the proposed administrative supplement with the caregivers of persons with bipolar disorder sampled in the parent study. This aim involves three separate analyses to compare the two groups of caregivers within each of the three treatment groups (education, resourcefulness training, and biofeedback) for each of the three health outcomes. For each intervention/treatment program, a two group by two time point RMANOVA will be used to determine differences within and between groups and the interaction of time × group. For example, one RMANOVA will examine differences between caregivers of persons with dementia and caregivers of person with bipolar disorders on health risks over two time points.

The third study aim (Aim #3), to explore differences between the two groups of caregivers in terms of their need for intervention (determined by baseline cut scores on study measures) and

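### Aim 2 compares dementia and bipolar caregivers, who are not randomised to caregiver type, without adjusting for caregiver sex or education, two factors that the protocol's own background links to intervention benefit

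*Combined protocol and SAP*

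**What the plan says.** The Background section, summarising a programme of multi-site dementia caregiver studies, says the tested interventions were "superior to control conditions for female versus male caregivers and for caregivers with lower versus higher education". It gives no effect sizes. It adds that those studies covered in-home caregivers only, and that "the interventions tested within the REACH projects did not include the implementation of biofeedback" or the skills that make up resourcefulness.

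Both factors are recorded. On screening, the Recruitment Methods section says: "We will also be collecting demographic information (gender, race, ethnicity, etc". On the study interviews, Study Design/Procedures says: "Demographic information will also be collected (e.g. occupation, annual income, education".

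The Data Analysis Plan uses neither factor. For Aim 1: "The primary analysis will be a three group × two time waves RMANOVA". Aim 2 is to "compare the two groups of caregivers within each of the three treatment groups", and for each treatment "a two group by two time point RMANOVA will be used to determine differences within and between groups and the interaction of time × group". The only factors in the Aim 2 model are caregiver type and time. The bipolar caregivers come from the parent study. No covariate, stratification, matching or weighting is described anywhere in the document.

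**The concern.** Participants are randomised to education, resourcefulness training or biofeedback. They are not randomised to caring for someone with dementia or with bipolar disorder. Each Aim 2 model therefore compares two samples recruited in different studies, and nothing in the design makes their sex or education mix alike.

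The Aim 2 term of interest is time by caregiver type, which compares mean change. A fixed difference in outcome level between men and women, or between education levels, cancels from it. A difference in response does not, and a difference in response is what the Background describes. If one sample has more of the better-responding caregivers, its mean change is larger for that reason alone, and the unadjusted model cannot separate this from caregiver type.

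The Background also says no published study has compared these two caregiver groups, so readers will have no earlier result against which to check the comparison.

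**Working it through.** The plan gives no figure for this point to reproduce: no alpha, power, effect size, SD, T1-T2 correlation, parent-study size or sample mix. The check therefore asks how large the distortion could be under stated assumptions.

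**Inputs from the documents**
- Group size: 90 caregivers (Study Design/Procedures) gives 90/3 = 30 per arm. The target of 100 (Number of Research Participants) gives 100/3, about 33. Equal allocation is assumed, since no ratio is stated.
- Model: caregiver type by time, fitted within one arm, with no covariates.

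**Assumptions**
- Mix gap between the two samples: 10 to 30 percentage points.
- Difference in response between levels of a factor: 0.3 to 0.5 SD of the outcome.
- Bipolar group: 30 per arm.
- T1-T2 correlation: 0.6.
- Two-sided alpha: 0.05.
- No true caregiver-type difference.

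**Spurious difference** = mix gap × response difference.
- Low end: 0.10 × 0.3 = 0.03 SD.
- Middle: 0.20 × 0.4 = 0.08 SD.
- High end: 0.30 × 0.5 = 0.15 SD.

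**False-positive rate**
- SD of change = √(2 × (1 − 0.6)) = 0.894 outcome SDs.
- Standard error of the difference in mean change, in SDs of change = √(1/30 + 1/30) = 0.258.
- Shift in the test statistic: z = (spurious difference / 0.894) / 0.258.
- Rejection rate = Φ(z − 1.96) + Φ(−z − 1.96).

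| Spurious difference (outcome SD) | z | False-positive rate |
|---|---|---|
| 0.03 | 0.13 | 5.2% |
| 0.08 | 0.35 | 6.4% |
| 0.15 | 0.65 | 10.0% |

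Using the t distribution at the high end gives 9.8%.

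**Sensitivity.** The next results are in SDs of change, which equal outcome SDs when the T1-T2 correlation is 0.5.
- A spurious difference of 0.15 gives 8.9% with 30 v 30, and 11.6% with 33 v 100 if the parent study is larger.
- If sex and education both differ in the same direction, by 30 points and 0.5 SD each, the spurious difference is 2 × 0.15 = 0.30 and the rate is 21% with 30 v 30. This stacks every unfavourable assumption and is an outer case.

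**Does adjustment work?** Putting sex in a model for change is equivalent to sex by time in the repeated-measures model. A simulation of 4,000 runs used 30 v 30, 80% v 60% women and a sex difference in change of 0.5 SD.
- Unadjusted: mean spurious difference about 0.10 SD, false-positive rate 6.9%.
- Adjusted: 0.00 SD and 5.1%.

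A main effect of sex alone would not do this, because it leaves the time by caregiver-type term unadjusted.

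**The case against.** **The evidence is indirect.** The cited studies tested neither biofeedback nor resourcefulness training, covered in-home dementia caregivers only, and say nothing about bipolar caregivers. They compared intervention with control, whereas Aim 2 compares pre-post change within one arm. This stands: a reader might infer that sex and education are established modifiers of the present interventions, but the Background makes that plausible and no more.

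**The size is assumed.** Nothing in the documents shows that the two samples differ in sex or education. In the lower half of the assumed range the false-positive rate is close to the nominal 5%. This also stands, and the high-end figure should not be quoted without the low end.

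**Aim 2 may be descriptive.** The protocol speaks of comparing responses and makes no causal claim. An unadjusted contrast legitimately describes how each sample responded. This is a good reason to keep the unadjusted result. It does not help a reader judge whether a difference is tied to caregiver type.

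**Two covariates do not remove confounding.** Other differences between the studies would remain, such as in-home versus facility care or the remote procedures introduced for COVID-19. This is true, and the report should say so.

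**Aim 1.** A reader might infer that Aim 1 has the same problem, since its model also omits both factors and its arms hold about 30 each. The documents do not support that. Allocation is random by computer, so the factors balance in expectation and the test's error rate already covers chance imbalance. A simulation with two arms of 30, 25% men and a 0.5 SD sex difference in change gave an unadjusted false-positive rate of 4.9%. Omission there may cost some precision but does not bias the comparison. Sex by time terms would also not address a sex difference in the arm effect.

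**Conclusion.** The point holds for Aim 2. The planned contrast is non-randomised and unadjusted, and it leaves out two recorded factors that the protocol itself connects with intervention benefit. Per factor, the potential distortion is 0.03 to 0.15 SD, with a false-positive rate of about 5% to 10% at 30 per group. Those figures rest on the assumed mix gaps, response differences, bipolar group size, T1-T2 correlation of 0.6 and two-sided alpha of 0.05.

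The documents show that Aim 2 could read a difference in mix as a caregiver-type difference. They do not show that it will. The effect is slight if the samples are similar or the factors matter little.

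**What to change.** In the Data Analysis Plan, for Aim 2:
- Add caregiver sex and education to each model, each with its interaction with time, and state how education is coded.
- Report the adjusted caregiver-type by time contrast alongside the unadjusted one.
- Tabulate sex and education by caregiver type, within treatment arm.
- State that a difference will be interpreted as related to caregiver type only if it persists after adjustment, and that other differences between the two studies remain uncontrolled.

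No change to Aim 1 is needed on this ground.

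The change is to analysis wording, and the dementia sample already supplies both items. The cost is two degrees of freedom if education enters as one term, more if it has several categories. There is also a small loss of precision when the mixes differ. With 80% v 60% women in equal groups, the correlation between caregiver type and sex is 0.05/(0.5 × √(0.7 × 0.3)) = 0.218. The standard error then rises by a factor of 1/√(1 − 0.218²) = 1.025, before any gain from variance that sex explains. The fix assumes that the parent study recorded both items in comparable form. The documents do not say so, and this should be confirmed first.

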Resourcefulness Training (RT) has been found effective in reducing stress, depressive cognitions, and negative emotions, and improving mental and physical health in older adults and caregiver populations, including dementia caregivers. The PI's pilot research with dementia caregivers shows they have a substantial need for resourcefulness skills as indicated by both subjective and objective measures, and that the RT intervention was found to be acceptable and feasible for dementia caregivers, particularly when it was tailored to meet their needs and preferences. The RT protocol with dementia caregivers was found to have implementation fidelity. Effect sizes on measures of caregiving responses (i.e., stress, depressive cognitions, and negative emotions) were found to be moderate to large when the dementia caregivers were given a choice in how they performed and reinforced resourcefulness skills.

The findings from this study have the potential to generate new scientific knowledge about the effectiveness of novel, easy to use, independently performed interventions that can be self-tailored to promote caregiver health through education, biofeedback, or resourcefulness. Once established, these health self-management interventions can be tailored to match the needs and preferences of other comparably distressed family caregivers of persons with other chronic mental or physical conditions.

Inclusion and Exclusion Criteria

Directions: Describe how individuals will be screened for eligibility. Using the tables below, describe the inclusion and exclusion criteria that will define who will be included and excluded in your final study sample.

| | Inclusion |
|----|------------------------------|
| 1. | English Speaking |
| 2. | At least 18 years old |

| | |
|----|---|
| 3. | Have a living family member with Alzheimer's disease or another dementia |
| 4. | Identify self as a primary caregiver |
| 5. | In-home caregivers: must be currently providing a minimum of 4 hours per day of supervision/direct care for at least the last 6 months. Caregivers whose family member lives within a facility: must report visiting their care recipient at least once per week for at least the last 6 months. |
| 6. | Be capable of performing informed consent and participating in study procedures. |

| Exclusion |
|--|
| 1. Does not have family member with Alzheimer's disease or another dementia. |

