| 2. Has not cared for a living family member for at least the last 6 months. |
| 3. Has knowledge of another family member in the same household enrolled in the study |
| 4. Currently pregnant |
| 5. Has a pacemaker |
| 6. Lives outside of the study area |

Number of Research Participants

Directions: Indicate the target number of research participants to be accrued locally, and, if this is a multi-site study, indicate the total number of research participants to be accrued across all sites.

Based on previous research by the PI and Co-Is, we conservatively estimate that ~20% of caregivers may not meet eligibility criteria. Thus, we will screen 125 participants to obtain the desired sample of size of 100.

Special/Vulnerable Populations

1. Indicate specifically if you will include each of the following special populations by checking the appropriate box:

- Adults unable to consent**
- Minors (infants, children, teenagers)**
- Wards of the state
- Foster Children
- Pregnant Women
- Neonates
- Neonates of Uncertain Viability
- Employees of CWRU or UHHS
- Prisoners
- Illiterate Individuals
- Non-English Speaking
- University Students

None

2. If the research involves individuals that are included in a special/vulnerable population, describe the additional safeguards included to protect the rights and welfare of the individuals for each population indicated.

If family caregivers who do not speak/understand the English language come forward with interest in participating and if they meet all other study criteria, we will make accommodations for translating the study measures and intervention materials or for having an interpreter provide appropriate explanations. If an illiterate individual comes forward with interest in participating and if they meet all other study criteria, we will make accommodations to dictate the consent form and all study questions. If a caregiver is an employee or student of CWRU, the consent form identifies participation in this research study as voluntary and if they choose not to participate, it will not affect their current or future relations with the university. No caregivers unable to consent will be enrolled. Adults unable to consent are only subjects to the extent that there is any identifiable information about them collected through the caregiver. They will not be present for any interventions or interactions.

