3. If excluding pregnant women, illiterate or non-English speaking individuals, provide a scientific rationale for the exclusion. Inconvenience or cost is not an acceptable rationale.

Pregnant women are excluded due to the measure of heart rate variability (HRV). The inclusion of pregnant women has the potential to alter the analyses that involve HRV measurement.

Recruitment Methods

Note: Attach all applicable recruitment materials to the last section of the Smart form under “Recruitment Materials.”

1. Which of the following methods will be used to recruit research participants. [Select all that apply](#)

- Email
- Phone call
- Letter
- Advertisement (e.g., poster, flyer, etc.)
- Social media
- Other. Please specify:

2. Describe when, where, and how potential research participants will be recruited.

The 100 family caregivers will be recruited from Cuyahoga County and 6 adjacent counties through social service advocacy agencies, community agencies, dementia care day programs and care facilities, and private physicians' offices who agree to provide us with access for posting / distributing information about the study. Agency personnel may assist us in identifying potential study participants who meet the following inclusion

criteria: caregivers will be at least 18 years old, report having a family member with dementia, and providing care or support for them for at least 6 months, but not necessarily in the same household (i.e. they may be living in a dementia care facility). However, we anticipate that most of the potential study participants will be those who see a posted advertisement or receive a flyer describing the study from one of agencies, centers, dementia care facilities, offices, etc., where we have permission to post / distribute information about the study. Contact information for the research office will be included on the flyers. Potential study participants will contact the research office for screening by a research team member to ensure he/she meets the eligibility criteria. If eligible, the team member will obtain their name, contact information (phone and/or email), address, and time / best method for the data collector to call to make an appointment to meet to discuss and enroll in the study, obtain their informed consent to participate, and conduct their first data collection interview.

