Within two weeks of the first data collection session, caregivers will be randomly assigned using a computer program to one of the three interventions (usual care/ education, resourcefulness, or biofeedback). Caregivers will receive the training and perform one health self-management intervention between the T1 and T2 data collections. The education, resourcefulness training, or biofeedback training will be introduced during a single face-to-face session in the caregiver's home/other private venue via a voice-over PowerPoint presentation presented on a tablet. All 90 caregivers who receive an intervention or usual care will keep a written log for the 4-week intervention period between the first (T1) and second (T2) data collection interviews. The caregivers will receive a pamphlet on their intervention (based on the PowerPoint presentation), a tracking log, and will receive telephone, email or text follow-up (preference of the study participant) for the next 28 days while performing the intervention independently and at their convenience. Interventionists will be carefully trained by Drs. [name] and [name] during a 2-day session that will include intervention delivery, cultural diversity training, and methods for providing psychological support/referral (e.g., "first call for help") in case caregivers experience psychological or physical distress during the training session or 28-day intervention period. Interventionists will be blinded to fidelity measures and different interventionists will provide education, resourcefulness training, and biofeedback; they will keep field notes and have weekly supervision by [name].

The first data collection session involves the additional measures of Financial Stress & Resourcefulness, and the second data collection adds an Intervention Evaluation Questionnaire that will ask participants for feedback regarding the intervention they received. Participants randomized to the Resourcefulness Training will be asked to complete the RT Skills Scale as part of the Intervention Evaluation Questionnaire.

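### Exclusion 3 screens for relatives by household rather than by care recipient, so relatives caring for one person from separate homes can be randomised to different arms, with a small risk of diluted contrasts

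*Combined protocol and SAP*

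**What the plan says.** **Eligibility** (Inclusion and Exclusion Criteria). Exclusion 3 removes a candidate who "Has knowledge of another family member in the same household enrolled in the study". No other criterion deals with related participants, and none limits enrolment to one caregiver per care recipient. Inclusion 4 asks that the person "Identify self as a primary caregiver", which is self-declared and can be true of more than one relative. Under Inclusion 5, in-home caregivers must give at least 4 hours of care a day, while facility caregivers "must report visiting their care recipient at least once per week for at least the last 6 months".

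**Recruitment** (Recruitment Methods, item 2). Care or support may be given "but not necessarily in the same household". Information is distributed in care facilities, among other places, and the protocol adds: "We will use snowball recruitment by asking study participants to refer others like them to the study". It expects most participants to come through posted advertisements or flyers.

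**Allocation and delivery** (Study Design/Procedures). After the first data collection, "caregivers will be randomly assigned using a computer program to one of the three interventions". Each caregiver receives one training session and a pamphlet, then practises independently for 28 days. To separate the arms, "different interventionists will provide education, resourcefulness training, and biofeedback".

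**Analysis** (Data Analysis Plan, Aim 1). "The primary analysis will be a three group × two time waves RMANOVA". No family or care-recipient term is mentioned.

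**The concern.** Two caregivers of the same person can be linked through the care recipient without sharing a home. Siblings who each visit a parent in a facility every week are the clearest case. Both meet Inclusion 5, both may call themselves a primary caregiver, and no reading of the household wording connects them. The protocol deliberately adds facility caregivers, and they are the group for whom the household link works least well. The rule also depends on what the candidate happens to know, so even a same-household relative could slip through.

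Once both are enrolled, nothing keeps them in the same arm. Pamphlets and self-practised skills pass easily between siblings. Using different interventionists per arm limits crossover through staff but not through family. If content is shared, the arms become more alike and a real difference is understated. A second, smaller issue is that the analysis treats relatives' responses as independent.

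**Working it through.** **Inputs from the protocol.** Target sample 100, about 20% of those screened ineligible, 125 to be screened (Number of Research Participants); 90 caregivers keeping a log, three arms, individual randomisation (Study Design/Procedures).

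**The plan's own figure.** 100 / (1 − 0.20) = 125, so the screening number reproduces. It is the only sample-size arithmetic given. There is no power statement, effect size, allocation ratio or expected number of related pairs.

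**Assumptions.** Allocation 1:1:1 and independent; k = 3, 5 or 10 related pairs among 100 caregivers. The share of participants in pairs is f = 2k/100 = 6%, 10% or 20%. A pair falls in different arms with probability 2/3.

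**Dilution if sharing is complete and effects add.** Let a, b and c be the three arm effects. A participant's relative is in each of the other two arms with probability 1/3, so:

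- Mean of arm A = a + (f/3)(b + c)
- Mean of arm C = c + (f/3)(a + b)
- Difference = (a − c)(1 − f/3)

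Exposure to the third arm cancels. The loss is f/3:

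- 3 pairs: 0.06/3 = 2.0%
- 5 pairs: 0.10/3 = 3.3%
- 10 pairs: 0.20/3 = 6.7%

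**Upper bound.** If every participant in a split pair contributes nothing to the contrast, the expected loss is 2f/3: 4.0%, 6.7% or 13.3%.

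**Illustrative effect on power.** Assumed: 30 per arm (90/3), pairwise comparison, two-sided 5%, normal approximation. Each range runs from the additive case to the upper bound.

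| | d = 0.8 | d = 0.5 |
|---|---|---|
| No pairs | 87.3% | 49.1% |
| 3 pairs | 85.9% to 84.5% | 47.5% to 46.0% |
| 5 pairs | 85.0% to 82.4% | 46.5% to 43.9% |
| 10 pairs | 82.4% to 76.6% | 43.9% to 38.9% |

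**Non-independence.** With two waves, the group × time test is equivalent to a one-way comparison of change scores. It was simulated with N = 90, no true effect, a within-pair correlation of change of 0.5 (deliberately high) and 15,000 runs. The Monte Carlo standard error is √(0.05 × 0.95/15,000) ≈ 0.2 percentage points.

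| Allocation of pairs | Type I error, about 10% in pairs | Type I error, about 20% in pairs |
|---|---|---|
| Individual randomisation (this design) | 5.3% | 4.9% |
| All pairs split across arms | 4.7% | 4.1% |
| All pairs in the same arm | 5.7% | 6.8% |

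If all pairs share an arm, the design effect is 1 + f × ICC. At f = 20% and ICC 0.5 it is 1 + 0.20 × 0.5 = 1.10. At f = 10% it is 1.05.

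**The case against.** The strongest reply is that related pairs may be rare. Inclusion 4 requires each person to see themselves as a primary caregiver, and the 4-hour daily minimum makes two qualifying in-home caregivers from separate homes unlikely. The route is therefore mainly the facility group, whose size is not given. Referral is of people like the participant, not of relatives, and most recruits are expected through advertisements. Complete sharing is also extreme, since each programme involves a training session and four weeks of logged practice. All of this stands. It limits the size of the problem but does not close the gap in the rule.

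A reader might also infer more than the documents support:

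- **That the primary test is invalid because it assumes independence.** Under individual randomisation the simulated error rate stays near 5%. Similarity between relatives that is stable over time cancels in the change from T1 to T2, so only correlated change matters.
- **That relatives' outcome scores describe the same patient.** Aim 1 outcomes are the caregiver's own health risks and physical and mental health. Dementia symptoms are collected but are not an Aim 1 outcome, and no burden measure is named.
- **That snowball recruitment is aimed at relatives, or that pairs have in fact enrolled.** The protocol says neither.

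**Conclusion.** The gap is real. Exclusion 3 is the only rule on linked participants, and it misses relatives of one care recipient who live apart. Individual randomisation can then place them in different arms. The consequence is a risk rather than an established fault, and mainly one of contamination toward no difference. For 3, 5 or 10 assumed pairs, the loss is about 2%, 3% or 7% of a contrast under complete sharing with additive effects, with upper bounds of 4%, 7% and 13%. Less than complete sharing would cost less. The figures rest on assumed pair counts and equal allocation, neither of which the documents state. Non-independence is secondary and does not by itself threaten the primary test. This is a cheap improvement, not a defect that undermines the trial.

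**What to change.** **Remaining recruitment.** Reword Exclusion 3 to: *another caregiver of the same care recipient is already enrolled, whether or not in the same household*. Add one question to the existing phone screen, and have staff check the answer against the screening log instead of relying on what the candidate knows. Staff should do this without disclosing that a relative is taking part.

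**Pairs already enrolled.** Enrolment was under way by the June 2021 update, so the new wording helps only later recruits. Keep all randomised participants in the primary analysis. Record a care-recipient identifier as a coded number, assigned before the identifying files are destroyed at the end of data collection. Report how many participants share an identifier. As a sensitivity analysis, compare change scores across arms with standard errors clustered on care recipient. Clustering addresses the correlation only; it does not undo contamination.

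**Cost.** One eligibility sentence, one screening question, one coded variable and one extra analysis, with an amendment to cover them. A few otherwise eligible relatives will be lost. The target of 125 to screen is unchanged if ineligibility stays near 20%; the documents give no basis for estimating how far the wider rule would raise it.
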